TABLE 1. TIMELINE OF KEY BNT162B2 REGULATORY MILESTONES

Vaccine formulation	Age group	Event
BNT162b2 monovalent XBB.1.5 COVID- 19 vaccine	Age 12 and older	11 September 2023: U.S. Food and Drug Administration (FDA) approval ²
	Age 6 months to 11 years	11 September 2023: FDA emergency use authorization (EUA) ²
	N/A	15 June 2023: (FDA)'s Vaccines and Related Biological Products Advisory Committee recommended that COVID-19 vaccines for 2023-2024 be updated to a monovalent XBB.1.5 vaccine. ³
BNT162b2 bivalent BA.4/5 COVID-19 vaccine	Age 12 and older	31 August 2022: FDA EUA ⁴
vaccine	Age 5 to 11	12 October 2022: FDA EUA ⁵
	Age 6 months to 4 years	08 December 2022: FDA EUA ⁶
BNT162b2 wild- type booster dose(s) COVID-19 vaccine	Age 5 to 11	17 May 2022: FDA authorized first booster dose
	Age 50 and older, and immunocompromised individuals	29 March 2022: FDA authorized second booster dose
	Age 65 and older, and individuals with potentially high risk that were age 18-64	22 September 2021: FDA authorized single booster dose
BNT162b2 wild- type primary series COVID-19 vaccine	Age 6 months to 4 years	17 June 2022: FDA EUA
	Age 5 to 11	29 October 2021: FDA EUA
	Age 16 and older Age 12 to 15	23 August 2021: FDA approval 10 May 2021: FDA EUA
	Age 16 and older	11 December 2020: FDA EUA

This protocol is not designated as a post-approval safety study (PASS) and is not a commitment to any regulatory bodies.

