8.7.3. Aim 3A

To estimate short-term healthcare resource utilization and costs associated with COVID-19 by vaccination status, age, and site of care.

Exposure: Persons will be considered vaccinated if they received the XBB.1.5 dose 14 or more days prior to admission. Persons will be considered unvaccinated if they had not received a dose.

Study Period: September 2023 – January 2024

Follow-up time: From admission (index date) to discharge.

Outcomes of interest: Similar to those in Somani, Firestone, Donnelley et al (2023)²²

- Cost of hospitalization
- Average length of stay, in days
- ICU admission
- Receipt of high-flow oxygen or mechanical ventilation
- Inpatient Mortality
- Use of antiviral treatment

Statistical Methods: All analyses will be pooled across California and Louisiana, and stratified by state. Descriptive statistics will be used to summarize patient characteristics, with mean (standard deviation) or median (25th percentile – 75th percentile) for continuous variables and counts (percentages) for categorical variables. Logistic regression will be used to estimate odds ratios (OR, with 95% CI) of ICU admission comparing vaccinated persons to unvaccinated persons. Linear regression with analysis of covariance (ANCOVA) will be used to compare costs of hospitalization for vaccinated and unvaccinated persons, and will be adjusted for age, and baseline characteristics. Results will be stratified by age groups.

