8.7.4. Aim 3B

To estimate long-term healthcare resource utilization and costs associated with COVID-19 by vaccination status, age, and site of care.

Exposure: Persons will be considered a COVID-19 patient if they experienced a COVID-19-related encounter, regardless of setting (cases). COVID-19 patients (cases) will be matched to 4 patients

without a COVID-19 diagnosis (controls) using the matched index date. Controls may or may not have had health care encounters during the study period. Cases and controls will be matched based on age, sex, insurance type, previous Charlson Comorbidity Index (CCI), number of previous hospitalizations, and follow-up time. The CCI and number of hospitalizations were calculated by using diagnoses during pre-index. For stratification/subgroup analyses, adult persons will be considered vaccinated if they received the BA.4.5 dose 14 or more days prior to index, persons will be considered unvaccinated if they had not received any COVID-19 vaccination doses. Children will be considered vaccinated if they received the any COVID-19 vaccination dose 14 or more days prior to index and will be considered unvaccinated if they had not received any COVID-19 vaccination doses.

Study Period (data including pre-index and follow-up): 01 June 2021 – 31 August 2023

Patient identification (index) window: June 2022 - November 2022

Follow-up time: starting 30 days after first COVID-19 diagnosis (index date) with follow-ups of 1 month, 3 months, 6 month, and 9 months.

Outcomes of interest: Similar to those in Pike et al, 2023

[figure not shown]
- All-cause direct healthcare costs (medical and pharmacy)
- All-cause Healthcare resource utilization
- COVID-19-related hospitalization (for cases only)

Statistical Methods: All analyses will be pooled across California and Louisiana, and stratified by state. Descriptive statistics will be used to summarize patient characteristics, with mean (standard deviation) or median (25th percentile – 75th percentile) for continuous variables and counts (percentages) for categorical variables. A regression model will be developed that adjusts for age, sex, and baseline comorbidities. We will stratify outcomes by vaccination status, healthcare cost (medical and pharmacy), and sites of care (inpatient, outpatient, etc.).

8.7.5. Aim 4

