5.2. Study Population

The study population will be comprised of adult (≥18 years of age) or pediatric (6 months to <18 years of age) patients who were diagnosed with COVID-19 between 01 June 2022 and 30 November 2022 and matched cohorts of control patients, who will be identified as those without a clinical diagnosis of COVID-19 during the matching time period. Patient matching will be described in greater detail in the latter section of the study protocol.

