- BNT162b2 Bivalent mRNA Vaccine: Patients who received at least one dose of a BNT162b2 Bivalent mRNA vaccine in the baseline period, at least 14 days prior to the index date.
- No Vaccine: Patients who did not receive any COVID-19 vaccines in the up to 12 months prior to the index date. For patients with baseline periods of less than 12 months, all available records in the past up to 12 months periods will be searched.
- Other Vaccines: Patients who were not in the above described 2 vaccination groups. They may include patients who received any type of COVID-19 vaccine in the up to 12 months prior to index date, but did not meet the BNT162b2 Bivalent Vaccine group requirements described above. Some examples of these include patients 1) who had other types of mRNA COVID-19 vaccine and no doses of a BNT162b2 Bivalent vaccine in the baseline period; 2) who received non-mRNA vaccines, etc.

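### Aim 3A's vaccinated-versus-unvaccinated contrast, and Aim 3B's summaries stratified by vaccination status, cover dates on which the vaccinated group cannot exist and state no calendar restriction or adjustment

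*Protocol*

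**What the plan says.** **Aim 3A (Protocol 8.7.3).** The study period is September 2023 to January 2024, without days. A patient is vaccinated if an XBB.1.5 dose was given at least 14 days before admission. Protocol Table 1 dates XBB.1.5 approval to 11 September 2023. Protocol section 7 makes inpatient expenditure, vaccinated versus unvaccinated, the main measure. The cost model "will be adjusted for age, and baseline characteristics". No adjustment is stated for the logistic model of ICU admission, and Protocol Table 5 lists no calendar variable.

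**Aim 3B window.** The Protocol gives "Patient identification (index) window: June 2022 - November 2022"; the Aim 3B SAP (5.2) takes patients "diagnosed with COVID-19 between 01 June 2022 and 30 November 2022".

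**Aim 3B vaccination status.** The Protocol says "adult persons will be considered vaccinated if they received the BA.4.5 dose 14 or more days prior to index". For the young it says "Children will be considered vaccinated if they received the any COVID-19 vaccination dose 14 or more days prior to index". The SAP (5.3) uses one rule for all ages: "at least one dose of a BNT162b2 Bivalent mRNA vaccine in the baseline period, at least 14 days prior to the index date". Its No Vaccine group has no COVID-19 vaccine in up to 12 months before index, which is possible on any day. For the bivalent vaccine at age 12 and over, Protocol Table 1 gives "31 August 2022: FDA EUA"; it gives 12 October 2022 for ages 5-11 and 8 December 2022 for ages 6 months to 4 years.

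**Aim 3B analyses.** The main measure compares COVID-19 with non-COVID-19 patients, matched on index date within 14 days. SAP 5.6 also stratifies utilization and cost by vaccination status (bivalent versus No Vaccine). The SAP regressions include both vaccination status and index year-month; the Protocol's Aim 3B model names age, sex and comorbidities only.

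**The concern.** If one group can be drawn from the whole window and the other only from its later part, a difference between them mixes vaccination with whatever changed over the window: season, circulating variant, and patterns of care and coding.

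In Aim 3A this reaches the main contrast. The Aim 1 SAP (5.7.5) itself dates XBB/JN.1 co-circulation from 9 December 2023 and estimates effectiveness by era. Aim 3A has no matching protection, although its vaccinated admissions tend to fall late.

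In Aim 3B, post-acute measurement starts 30 days after index. It can begin on 1 July 2022 for an unvaccinated adult, but not before 14 October 2022 for a vaccinated one. The 1-month and 3-month windows of the two strata therefore sit in different seasons. A reader who compares the strata, as the objective invites, could credit vaccination with a seasonal difference.

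**Working it through.** **The plan's own figure.** The only power statement for Aim 3 (Aim 3B SAP 5.5: above 0.99) concerns cases versus controls. It reproduces. With 50,000 cases, 200,000 controls, and 50% versus 40% having non-zero cost, the pooled proportion is (25,000 + 80,000)/250,000 = 0.42, and z = 0.10/√(0.42 × 0.58 × (1/50,000 + 1/200,000)) = 40.5. It says nothing about vaccination strata, for which no figure is given.

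**Blocked days.** First vaccinated date = authorization date + 14 days. Blocked days = days in the window before that date.

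| Group and definition | First vaccinated date | Blocked / window | Days left |
|---|---|---|---|
| 3A, start 1 Sep 2023 (assumed) | 25 Sep 2023 | 24/153 = 16% | 129 |
| 3A, start 11 Sep 2023 (assumed) | 25 Sep 2023 | 14/143 = 10% | 129 |
| 3B, age 12+, bivalent | 14 Sep 2022 | 105/183 = 57% | 78 |
| 3B, age 5-11, SAP bivalent | 26 Oct 2022 | 147/183 = 80% | 36 |
| 3B, 6 months-4 years, SAP bivalent | 22 Dec 2022 | 183/183 = 100% | 0 |
| 3B, age 5-17, Protocol any dose | before the window | 0/183 | 183 |
| 3B, 6 months-4 years, Protocol any dose | 1 Jul 2022 | 30/183 = 16% | 153 |

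The last two rows use the wild-type authorizations in Protocol Table 1 (29 October 2021 or earlier for age 5 and over; 17 June 2022 for the youngest).

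**Aim 3A: share of admissions on or after 9 December 2023.** Assume flat admissions to 31 January 2024, which leaves 54 days from 9 December.

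- Vaccinated, coverage flat from 25 September: 54/129 = 42%.
- Vaccinated, coverage rising linearly over n possible days, k of them before 9 December: share = 1 − k(k+1)/(n(n+1)).
  - From 25 September: 1 − (75 × 76)/(129 × 130) = 66%.
  - From 9 October (dosing starts 14 days after approval, the uptake pattern assumed in the Aim 1 precision simulation): 1 − (61 × 62)/(115 × 116) = 72%.
- Unvaccinated, with final coverage of 9.6% (16% × 60%) to 16% reached on 11 March 2024 in the linear cases or held from 25 September in the flat case: about 34-35% with a 1 September start and 36-37% with an 11 September start.

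**Aim 3B, age 12+: shift in mean index date.** Assume uniform case incidence. The unvaccinated mean is 31 August. The vaccinated mean is 22 October if coverage is flat (52 days later). If coverage rises linearly, the mean offset is 2(78 − 1)/3 = 51 days after 14 September, which is 4 November (65 days later).

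**The case against.** The other side has several good points.

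- **Aim 3B's main result is safe.** Cases and controls are matched within 14 days. A reader might infer that the aim as a whole is confounded by season; the documents do not support that. Vaccination status is a stratifier, and no formal test between strata of the descriptive summaries is specified.
- **The SAP regression already handles calendar time** through index year-month. Under the SAP definition, June to August 2022 still contains no vaccinated patients and adds no direct information on the vaccination contrast, but the adjustment is there. What remains is the unadjusted stratified summaries.
- **It is tempting to say that nobody could be vaccinated when the Aim 3B window opens.** That is wrong for children aged 5 and over under the Protocol, which counts any COVID-19 dose. It is right for adults, and for all ages only under the SAP's bivalent rule.
- **The Aim 3A SAP is not in the set**, and Protocol 8.7 defers detail to SAPs. The missing calendar term is shown at Protocol level only.
- **The 66-72% figure rests on linear uptake**, an assumption borrowed from a precision simulation and not a forecast. With flat coverage the contrast is 42% against about 34-37%.
- **Season weighs less in the longest Aim 3B window** (330 days) for patients followed throughout.

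These points narrow the concern. They do not remove it from Aim 3A's main contrast, where date matching and year-month adjustment are both absent from the stated plan, or from the Aim 3B stratified summaries.

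**Conclusion.** The point holds in limited form.

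- **Aim 3A:** 10-16% of the period cannot contain a vaccinated admission, and rising uptake adds imbalance after that. Between 42% and 72% of vaccinated admissions, against about 34-37% of unvaccinated ones, would fall on or after 9 December 2023. The blocked days follow from the documents' dates plus an assumed start day; the shares also assume flat admissions and the uptake shapes shown.
- **Aim 3B:** the stratified summaries by vaccination status set a No Vaccine stratum from 183 days against a vaccinated stratum from 78 days (age 12+). Under the SAP definition the vaccinated stratum has 36 days at ages 5-11 and none at 6 months to 4 years.

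A reader might go further and infer that the results are biased for or against the vaccine. Nothing in the documents supports a direction or a size: they date the variant eras but give no effect of era or season on ICU use or cost.

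**What to change.** **First**, reconcile the pediatric vaccinated definition between Protocol 8.7.4 (any dose) and the Aim 3B SAP 5.3 (bivalent). The pediatric date limits below apply only under the SAP definition.

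**Aim 3A.** Start the vaccinated-versus-unvaccinated comparison at admissions from 25 September 2023, and add admission month to both the logistic and the cost model. The date limit alone is not enough: under linear uptake, 66-72% of vaccinated admissions would still fall on or after 9 December, against at most 54/129 = 42% of unvaccinated ones. State the adjustment set for the ICU model too.

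**Aim 3B.** For the vaccination-status stratification only (both strata, cases and controls), restrict index dates to 14 September 2022 onward for age 12 and over, and 26 October 2022 onward for ages 5-11. Preferably also standardize both strata to a common index-month distribution. Report no bivalent stratum for ages 6 months to 4 years.

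**Cost.** SAP wording, a date filter and one covariate (five calendar months, so four degrees of freedom). Aim 3A loses unvaccinated admissions from 14 to 24 days. The Aim 3B stratification loses the No Vaccine patients indexed on the first 57% of days (age 12+) or 80% of days (ages 5-11, SAP definition), from an expected cohort of more than 50,000 cases. All other Aim 3B analyses keep the full window.

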8.8. Quality Control

Data in HealthVerity's database are provided monthly in an electronic format. HealthVerity employs its foundational product to match patients between different data sources with high accuracy. All analyses will be performed internally and according to Pfizer analytic standards, including double programming to ensure quality control.

8.9. Limitations of the Research Methods

- This analysis is from two states and thus may not generalize to other areas of the country.
 California is the largest and most populous state in the US (approximately the size of Canada), which afford unique opportunities with study population size. Louisiana represents a different geographical region of the country, where there may be varying patterns of individual health characteristics and health seeking behaviors.
- We do not have laboratory confirmation of the COVID-19 diagnosis, therefore it is possible
 that some patients are being diagnosed with symptoms alone or that we are missing positive
 cases due to at-home testing.
- The results from this study may differ from those of VE studies using other data sources, such as Kaiser Permanente of Southern California.
- Exposed patients may have varying times since vaccination, and VE may wane over the 6
 months of follow-up, which could bias the results towards the null.
- Attempts to address confounding may not be able to fully account for confounders.

8.10. Other Aspects

Not applicable.

9. PROTECTION OF HUMAN PARTICIPANTS

9.1. Patient Information

This study involves data that exist in deidentified/anonymized structured format and contain no patient personal information.

9.2. Patient Consent

As this study involves deidentified/anonymized structured data, which according to applicable legal requirements do not contain data subject to privacy laws, obtaining informed consent from patients by Pfizer is not required.

9.3. Institutional Review Board (IRB)/ Ethics Committee (EC)

This study uses de-identified data. As such this study will be submitted to an IRB for exemption under category 4, pursuant to the terms of the US Department of Health and Human Service's Policy for Protection of human Subjects at 45 C.F.R 46.104(d).

9.4. Ethical Conduct of the Study

The study will be conducted in accordance with legal and regulatory requirements, as well as with scientific purpose, value and rigor and follow generally accepted research practices described in CT24-WI-GL02-RF04 including Guidelines for Good Pharmacoepidemiologic Practices (GPP) and the European Medicines Agency (EMA) European Network of Centres for Pharmacoepidemiology and Pharmacovigilance (ENCePP) Guide on Methodological Standards in Pharmacoepidemiology.

10. MANAGEMENT AND REPORTING OF ADVERSE EVENTS/ADVERSE REACTIONS

This study involves the use of databases which consist of data that existed as structured data at the time that the study started. In this data, individual patient data are not retrieved or validated, and it is not possible to link (ie, identify a potential association between) a particular product and medical event for any individual. Thus, the minimum criteria for reporting an adverse event (AE) (ie, identifiable patient, identifiable reporter, a suspect product, and event) cannot be met.

11. PLANS FOR DISSEMINATING AND COMMUNICATING STUDY RESULTS

For all publications relating to the study, Pfizer will comply with recognized ethical standards concerning publications and authorship, including Section II - "Ethical Considerations in the Conduct and Reporting of Research" of the Uniform Requirements for Manuscripts Submitted to Biomedical Journals, http://www.icmje.org/index.html#authorship, established by the International Committee of Medical Journal Editors.

In the event of any prohibition or restriction imposed (eg, clinical hold) by an applicable competent authority in any area of the world, or if the party responsible for collecting data from the participant is aware of any new information which might influence the evaluation of the benefits and risks of a Pfizer product, Pfizer should be informed immediately.

ANNEX 1. LIST OF STANDALONE DOCUMENTS

None.

ANNEX 2. ENCEPP CHECKLIST FOR STUDY PROTOCOLS

This study is not a PASS protocol submitted in the EU/EEA or UK, and thus this annex is not required.

1. AMENDMENTS FROM PREVIOUS VERSION(S)

NA. First version.

2. LIST OF ABBREVIATIONS

Abbreviation	Definition		
aHR	Adjusted hazard ratio		
CDC	Centers for Disease Control and Prevention		
CI	Confidence interval		
CPT	Current Procedural Terminology®		
CVX	Clinical Vaccines Administered code		
EUA	Emergency use authorization		
FDA	U.S. Food and Drug Administration		
HV	HealthVerity		
ICD-10-CM	International Classification of Diseases, Tenth Revision, Clinical Modification		
ICU	Intensive care unit		
NDC	National Drug Codes		
RSV	Respiratory syncytial virus		
SAP	Statistical Analysis Plan		
SMD	Standardized mean differences		
NPI	National provider identifier		
VE	Vaccine effectiveness		

BNT162b2 (COVID-19 vaccine formulations)
C4591065 NON-INTERVENTIONAL STUDY STATISTICAL ANALYSIS PLAN FOR SECONDARY DATA
COLLECTION STUDY
SAP version 1.0, 10 June 2024

Note: in this document, any text taken directly from the non-interventional (NI) study protocol is *italicized*.

3. RATIONALE AND BACKGROUND

Until recently, vaccine registries were not available for de-identification and linkage to secondary claims-based databases. However, through a collaboration with HealthVerity, a leading supplier of secondary health data, the State of California and the State of Louisiana have made their vaccine registries available for linkage for research purposes. California and Louisiana deidentify the registries, using HealthVerity's software to convert each patient's protected health information to a unique HealthVerity ID which can then be linked to the full HealthVerity database to gather clinical history and outcomes.

The purpose of this document is to detail the statistical methods and analyses that will be used in the HealthVerity claims database linked to the State of California/Louisiana's vaccine registries to address Aim 2 of the study protocol. Separate SAPs will be produced to address the other aims of the protocol.

4. STUDY OBJECTIVES AND HYPOTHESES

The objective of Aim 2 of this study is to assess the vaccine effectiveness (VE) of BNT162b2 formulations in pediatrics against medically attended COVID-19, non-COVID-19 respiratory infections, mortality and healthcare resource utilization by age and adapted vaccine formulation.

This study is descriptive in nature and as such does not include any pre-specified hypotheses.

5. RESEARCH METHODS

5.1. Study Design

This will be a retrospective cohort study using data from patients who were California or Louisiana residents in the HealthVerity claims database.

Cohort identification will begin from the date of Emergency Use Authorization (EUA) or U.S Food and Drug Administration (FDA) approval for the BNT162b2 formulation. Study follow-up will occur from FDA EUA or approval date until COVID-19 diagnosis or other outcome of interest (hospitalization, emergency department visit, outpatient encounter, end of medical and/or pharmacy enrollment, or death [according to the mortality database]).

The authorization/approval dates for each BNT162b2 formulation that will be used in this study are provided in Table 5.1.

Table 5.1 Timeline of Key BNT162b2 Regulatory Milestones Applicable to Pediatrics

Vaccine formulation	Age group	Event
BNT162b2 monovalent	Age 12 and	September 11, 2023: U.S. Food and Drug
XBB.1.5 COVID-19 vaccine	older	Administration (FDA) approval
	Age 6 months to 11 years	September 11, 2023: FDA emergency use authorization (EUA)
BNT162b2 bivalent BA.4/5 COVID-19 vaccine	Age 12 and older	August 31, 2022: FDA EUA
	Age 5 to 11	October 12, 2022: FDA EUA
	Age 6 months to 4 years	December 8, 2022: FDA EUA

All persons will be considered unvaccinated from date of FDA date of vaccine authorization/approval until, where applicable, 13 days after receipt of vaccine. In order to allow for time after dose for meaningful immunologic protection to accrue, persons will be considered vaccinated 14 days after vaccination.

The following data are available, from 01 December 2018, with varying look-back periods as outlined below to define patient's characteristics, clinical history, risk factors, and healthcare utilization.

The outcomes of interest are medically attended COVID-19, non-COVID-19 respiratory infections, mortality and healthcare resource utilization and are described in Table 5.2.

Main summary measure: VE = (1 - adjusted hazard ratio [aHR]) * 100, comparing vaccinated to unvaccinated persons

